Primary outcome is systolic BP at 12-months, which is the major modifiable step to stroke event rate reduction. A secondary analysis will examine whether PACESETTER improved systolic BP by a clinically significant amount. Also apart from the 12 month primary outcome, we will also conduct a longitudinal comparisons of systolic BP in IG vs. SC over the course of followup evaluations. Participants will be given an appointment encounter solely for collecting evaluation data at the times listed in Figure 2. Trained assessors blinded to the randomization arm (with no contact with PACESETTER clinical team and instructed not to infer and probe on the intervention) will perform all study measurements. Potential mediator/moderators of risk factor control will also be collected. If a patient endorses severe depressive symptoms, patient will be referred to the appropriate medical professional.

Table 3. PACESETTER Outcomes and Mediators

Outcome Type	Measurements	Assessment Duration	Target Goal	Baseline	4 months	8 months	12 months
Primary	Systolic blood pressure ^{173,174}	<15 mins	< 130 mmHg	X	X	X	X
Secondary	Cardiovascular ED encounters and re-hospitalizations	<10 mins	Group differences	X	X	X	X
	Medication adherence ¹²⁵	<10 mins	Group differences	X	X	X	X
	Body mass index ¹²⁶	<5 mins	Group differences	X	X	X	X
	Self-management ^{127,128}	<10 mins	Group differences	X	X	X	X
Tertiary	Stroke, Myocardial infarction, Death	<10 mins	Group differences	N/A	X	X	X
Mediators	Age, education, income, depression, ^{129,130}	<5 mins	Group differences	X	N/A	N/A	N/A
	HTN/stroke Knowledge, ^{131,132} Health literacy, ^{133,134} disability, ^{135,136} and study site	<10 mins	Group differences	X	X	X	X
	Side effects, Adverse events (as reported)	<10 mins	Group differences	X	X	X	X

E.5.5.1. Physiological/Laboratory Measures

i. BP measurements: Three readings will be taken by trained assessors (if patient is unable to be seen in person, trained assessor will confirm the readings are taken correctly by patient either by verbal confirmation of procedures or visually watching the patient complete the BP measurements) using an automated BP monitor with the patient seated comfortably for 5 min prior to the measurements, following guidelines.^{137,138} Average of the last two BP readings will be used as the measure for each visit. Uncontrolled BP is defined as average clinic systolic BP ≥ 130 mm Hg or diastolic BP ≥ 90 mmHg per guidelines.¹³⁷

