iv. Chart extraction: Information extracted from the medical records will include medications and their dosages, biomarker measurements from clinic visits, and medical comorbidities.

E.5.5.3. Vascular Events (Specific Aim 3)

PACESETTER aims to collect any vascular events that take place while a patient is in the trial. This is being done to ensure that all events are captured in a timely fashion without any recollection biases. In order to do this, all participants & families will be urged to contact the RC as soon as any event that might be a CVD event

Program to Avoid Cerebrovascular Events through Systematic Electronic Tracking and Tailoring of an Eminent Risk-factor (PACESETTER)

has occurred. CVD events will include stroke, transient ischemic attack, or an acute coronary syndrome. Participants with potential CVD events will be evaluated by a study physician within 48 hours. If the history or the exam indicates that a stroke might have taken place, all clinical, laboratory & imaging data needed to confirm the event will be obtained by the RC & sent to a blinded physician adjudicator assigned to each site (see letters of support), for independent review. Final reports regarding the event will be sent to primary research site (MUSC) within 15 days. Participants with events will continue to be followed at scheduled intervals. These are study-specific steps the patient or caregiver will be asked to take once the CVD event has been addressed medically- ie, after the condition been treated and stabilized.

E.5.6. Statistical Considerations

E.5.6.1. Randomization

Once eligibility, consent & baseline data are confirmed, participants will be randomly assigned to PACESETTER intervention vs. usual care in a 1:1 allocation ratio, stratified by race (Black and White) & study site. An adaptive block randomization scheme will be developed & maintained by the lead study biostatistician. Once a patient is randomized he or she will be entered into the study and included in intent-to-treat analysis. The randomization assignment will be known to the project coordinator, and the statistician in charge of the randomization procedure, but not known to the research assistant who will be conducting participant follow-up assessments.

E.5.6.2. Power and Sample Justification

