Our sample size calculation and power analyses are based on a 12 month change in the primary outcome of SBP, the premier modifiable risk factor for stroke. Large meta-analyses of observational and RCTs have found clinical benefit for having a SBP as low as 115 mm Hg. In addition, a large RCT of SBP-lowering for secondary stroke prevention found similar health benefits for persons with baseline HTN and for persons with baseline normotension. Data from MUSC clinic registry showed that the mean SBP for persons with SBP>120mmHg was 154.5 +/-10.3 mmHg. Using a type I error of 0.05, a power of 92%, a robust correlation of 0.8 between baseline and 12-months outcomes, no change in mean SBP in the control arm from baseline to 12 months and a two-sided test, 80 subjects in each treatment arm (or 160 subjects in total) will enable detection of a net decrease of 0.5 standard deviation units (which correspond to a difference of 8.8 mm Hg in SBP). This difference of 8.8 mm Hg in SBP between the two treatments is smaller than the 10 mm Hg threshold cited in the guideline, and thus we have sufficient statistical power with the estimated sample size to detect clinical benefit. An alternative outcome measure to SBP is recurrent stroke, but our sample size is not large enough to detect differences in recurrent stroke over 12-months of follow-up. Although we will facilitate the retention of subjects in the RCT as much as possible, the retention rates in disadvantaged populations are likely lower than in other settings. Assuming 20% loss to follow up, the conservative target for enrollment is 200. Data from MUSC indicated that 85% of all the patients at 3 days post-stroke had a SBP > 120. Thus, we conservatively expect ~50% will not meet eligibility criteria or may decline to participate, so we can potentially recruit over 200 patients including half of whom will be African Americans from the 2 sites over 3 years.

E.5.7. Data Management and Analysis

E.5.7.1. Analysis

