Descriptive statistics will be computed for all study variables, including average follow-up time, retention rate, protocol deviations and violations, and will be compared by treatment group. We will use t-test for continuous variables and chi-square test for categorical variables to make comparisons between two groups and corresponding ANOVA for more than two groups. The primary analysis will be performed according to the principle of intention to treat. All outcomes will be modeled using regression analyses adjusted for baseline factors that show imbalance after randomization and compared to analysis that does not adjust for residual baseline differences.^{140,141} A nominal p value of 0.05 or less will be considered as statistically significant in the primary analysis. Analysis of covariance (ANCOVA) will be used to test the hypotheses in Aim 2 adjusting for baseline differences. Assessment of the fit of the models will be made using residual and diagnostic plots. We will employ longitudinal data methods (generalized linear mixed models [GLMM]),¹⁴² which account for correlation of outcomes due to repeated measurements and clustering by site and missing at random (MAR) data to study the change in outcomes over time between the two groups. In addition, to evaluate sensitivity of study conclusions to missing data, we will use multiple imputation methods to estimate single end-point outcome measures and carry out analyses on the complete data set using the MNAR statement in SAS 9.4. If we suspect violation of MAR then we will do additional sensitivity analysis.¹⁴³ Trajectory or change over time in BP and other related outcomes will be modeled via GLMM. Differences in time to recurrent events between the two groups will be compared using a log-rank test and a Cox proportional hazards (PH) model (we will test for the PH assumption) will be used to adjust for observed confounders. Since all participant data will be included in this analysis, participants missing outcome data will be censored at the last follow-up assessment time. Exploratory analyses will also be performed by sub-groups (e.g. age, gender, race) to determine if any differential efficacy exists. If statistically significant differences are found between IG and CG arms, we will conduct regression analyses further adjusted by variables selected based on a combination of clinical judgment and descriptive statistical findings comparing

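### No stated primary model for 12-month systolic BP includes baseline BP, race or site regardless of balance: covariates follow an undefined imbalance rule, and neither the adjusted nor the unadjusted result is labelled primary

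*Combined protocol and SAP*

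**What the plan says.** All references are to the combined protocol and SAP.

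- **E.5.7.1 (Analysis).** All outcomes are to be modelled by regression "adjusted for baseline factors that show imbalance after randomization and compared to analysis that does not adjust for residual baseline differences". No test, threshold or list of candidate factors defines imbalance. The nearest hint is the sentence on group comparisons: "We will use t-test for continuous variables and chi-square test for categorical variables to make comparisons between two groups". The label of primary analysis is attached to intention to treat and to a p value of 0.05 or less, not to the adjusted or the unadjusted model.
- **E.5.7.1, ANCOVA.** It is named for one purpose: "Analysis of covariance (ANCOVA) will be used to test the hypotheses in Aim 2 adjusting for baseline differences". Aim 2 (E.5) concerns emergency department encounters and re-hospitalizations, not SBP.
- **E.5.7.1, mixed models.** These are said to "account for correlation of outcomes due to repeated measurements and clustering by site" and to deal with data missing at random (MAR), for change over time.
- **E.5.5 (Outcomes).** "Primary outcome is systolic BP at 12-months". The repeated-measures comparison is set to one side: "Also apart from the 12 month primary outcome, we will also conduct a longitudinal comparisons of systolic BP in IG vs. SC".
- **E.5.6.1 (Randomization).** Allocation is 1:1, "stratified by race (Black and White) & study site".
- **E.5.6.2 (Power).** The calculation refers to a 12-month change in SBP and assumes "a robust correlation of 0.8 between baseline and 12-months outcomes".

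**The concern.** A baseline covariate adds precision through its correlation with the outcome, not through being out of balance. Baseline SBP is the strongest predictor the plan names, yet under E.5.7.1 it enters the regression for 12-month SBP only if it meets an unstated imbalance criterion. Race and site are balanced by the stratified randomisation, so a p-value criterion would almost never select them, although they are the factors the design was built around.

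Two things are at stake. One is precision that could be had from data already collected. The other is clarity: there are two results for the same outcome, and no statement of which one tests the primary hypothesis.

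**Working it through.** **Inputs from E.5.6.2:** n = 80 per arm analysed, effect d = 0.5 SD, two-sided alpha 0.05, r = 0.8, effect 8.8 mm Hg, so the implied SD is 8.8/0.5 = 17.6 mm Hg.

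**Assumed, because the plan gives no value:** four imbalance criteria (baseline p<0.05, p<0.10, p<0.20, standardised difference >0.1), lower correlations of 0.5 and 0.3, and block sizes of 4 or 8.

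**Step 1. The plan's 92%.** Power comes from the noncentral t distribution with noncentrality d/(k × sqrt(2/n)), where k is the residual SD as a multiple of the outcome SD.

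- Unadjusted, k = 1: 0.5/0.1581 = 3.16, power 88%.
- Change score, k = sqrt(2(1 − 0.8)) = 0.632: noncentrality 5.00, power 99.9%.
- ANCOVA, k = sqrt(1 − 0.8²) = 0.6: noncentrality 5.27, power 99.9% (155 df with race and site terms).

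None of these gives 92%. A time-averaged repeated-measures formula with variance factor (1 + (m − 1) × 0.8)/m comes close: 91.5% for m = 2 readings and 92.5% for m = 3 (normal approximation). The plan describes no such analysis. The enrolment figure does reproduce: 160/0.8 = 200.

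**Step 2. The imbalance rule for a 12-month level.** These are 100,000 simulated trials per cell, bivariate normal, 80 per arm.

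| Criterion (assumed) | Baseline SBP enters | Power, r = 0.8 | Power, r = 0.5 | Power, r = 0.3 | Null rejection, r = 0.8 |
|---|---|---|---|---|---|
| p<0.05 | 5% | 90% | 89% | 89% | 3.1% |
| p<0.10 | 10% | 92% | 90% | 89% | 2.4% |
| p<0.20 | 20% | 94% | 91% | 89% | 1.9% |
| Std. difference >0.1 | 53% | 98% | 93% | 90% | 2.8% |
| Never (unadjusted) | 0% | 88% | 88% | 88% | 5% |
| Always (ANCOVA) | 100% | 99.9% | 95% | 91% | 5% |

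Share of the available power gain kept at r = 0.8, as (rule − 0.882)/(0.9996 − 0.882):

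- p<0.05: 0.021/0.118 = 18%
- p<0.10: 0.037/0.118 = 31%
- p<0.20: 0.060/0.118 = 51%
- standardised difference >0.1: 0.099/0.118 = 84%

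**Step 3. Precision.** Half-width = t(0.975) × 17.6 × k × sqrt(2/80).

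- Unadjusted: 1.975 × 17.6 × 0.1581 = 5.5 mm Hg.
- ANCOVA: 5.5 × 0.6 = 3.3 mm Hg at r = 0.8 (4.8 at r = 0.5, 5.2 at r = 0.3).
- Change score: 5.5 × 0.632 = 3.5 mm Hg at r = 0.8.

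In sample-size terms, ANCOVA at 80 per arm matches 80/(1 − r²) per arm unadjusted: 222 at r = 0.8, 107 at 0.5, 88 at 0.3.

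**Step 4. Change score at lower r.** At r = 0.5, k = 1 and power is 88%, the same as unadjusted. At r = 0.3, k = 1.183 and power falls to 76%.

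**Step 5. Two results, no label.** With a true 0.5 SD effect and r = 0.8, the rule-based and unadjusted results disagree on significance in 2%, 4%, 6% or 10% of trials under the four criteria. Under the null, if the better of the two were taken, rejection would be 5.1%, 5.2%, 5.5% or 6.5%, and about 7.5% for a criterion of standardised difference >0.05. A free choice between always-adjusted and unadjusted gives about 8.7%.

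**Step 6. Race and site.** In 3,000 simulated trials of 200 participants (two races and two sites at 50% each, blocks of 4 or 8), neither factor met p<0.05 among all randomised in any trial.

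**The case against.** Several points on the other side have force.

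- **Baseline SBP may enter by another route.** A reader might infer that it is used only by chance. The documents do not support so firm a statement. E.5.6.2 speaks of a 12-month change, and if change is the analysed outcome, baseline enters through the outcome itself, with almost no loss at r = 0.8. E.9.3 describes the primary intention-to-treat estimates as resting on MAR, and in E.5.7.1 the model described as handling MAR data is the mixed model, which would use baseline SBP if it is one of the repeated measures. Neither hint settles the matter, since E.5.5 defines the outcome as the 12-month value and sets the longitudinal comparison apart. Nor is the change score a safe default, as step 4 shows.
- **The adjusted model reads as the lead.** That is the natural sense of the sentence. It would settle the label but not the selection of covariates.
- **The test is valid.** A reader might infer inflated type I error. The rule alone rejects less than 5% of the time under the null. Inflation needs a choice of the more favourable result after the data are seen, and the plan does not say that would happen.
- **The loss may be small.** A reader might infer that most of the gain is always lost. At p<0.20 about half the power gain is kept, at a standardised difference >0.1 most of it, and at r = 0.3 there is little to gain.
- **Scope.** Aim 1 in E.5 describes the primary outcome as achieving SBP control, a binary outcome. None of these figures applies to that.
- **Cited references.** The adjustment sentence cites sources that may define its approach. They could not be consulted.

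**Conclusion.** The point stands as a should-fix matter of efficiency and specification. The plan defines no imbalance criterion, does not label the adjusted or unadjusted result primary, and states no primary model with baseline SBP, race and site included regardless of balance.

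For continuous 12-month SBP at the plan's own r = 0.8, the imbalance rule forgoes about half or more of the available power gain under p-value criteria, and little under a standardised difference >0.1. Even the unadjusted analysis has 88% power, so the trial is not badly underpowered on its own inputs. The larger cost is a wider interval than the data require.

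The rule-based figures rest on assumed criteria, and the results at r = 0.5 and 0.3 on assumed correlations. The mm Hg figures use SD 17.6, which 8.8 mm Hg as 0.5 SD implies. The registry SD in E.5.6.2 is 10.3, and with it every half-width shrinks in proportion (about 3.2 unadjusted and 1.9 with ANCOVA at r = 0.8).

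**What to change.** In E.5.7.1, delete the selection of covariates by imbalance and state one primary analysis for continuous 12-month SBP: all randomised participants, with baseline SBP (continuous), race and site as covariates regardless of balance, tested two-sided at 0.05. Choose one of two forms:

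1. The 12-month contrast from the repeated-measures model that E.5.7.1 already describes as handling MAR data.
2. ANCOVA with multiple imputation under MAR. E.5.7.1 names imputation only for sensitivity analysis, so the text should say that it moves to the primary analysis.

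Label the unadjusted result a sensitivity analysis. Restate power in E.5.6.2 with the formula for the chosen model over a range of correlations. For ANCOVA with 80 per arm and 0.5 SD this is 91%, 95% and 99.9% at r = 0.3, 0.5 and 0.8.

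The cost is SAP wording and a revised power paragraph. Baseline SBP, race and site are already collected, so no patients, visits or data are added.

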A clinically-effective PACESETTER intervention, if scaled, could potentially: a) reduce stroke morbidity, mortality, and associated costs after stroke in the stroke buckle and US, b) be applicable to CVD risk reduction for patients with other major CVD entities such as coronary artery disease, congestive heart failure and chronic kidney disease, and c) bridge racial, regional, and rural disparities in stroke outcomes. PACESETTER will be assessed at the three key tertiary healthcare system in the entire state of South Carolina. These

geographically dispersed hospitals (Figure 1) are all affiliated with universities supported by the State Government and serve as Safety Net facilities for the poor and underserved including race-ethnic minorities and rural dwellers. As such a positive outcome will likely have the buy-in of healthcare policy makers at all levels in the State, thereby increasing the chances of sustainability of the intervention in routine clinical practice beyond the period of study funding. On the other hand, even if PACESETTER has no effect, pre-planned analyses will allow us to discriminate aspects of the intervention that may have been otherwise effective, as well as understand differences in efficacy and acceptability within our cohort such that more appropriately designed risk prevention studies can be developed in the future. When we have completed this RCT, we plan to make the products from PACESETTER available to the research and public health community.

C. PRELIMINARY DATA

C.1. Prelim Data #1: Using Mobile Health to modify risk factors for stroke prevention

Program to Avoid Cerebrovascular Events through Systematic Electronic Tracking and Tailoring of an Eminent Risk-factor (PACESETTER)

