Program to Avoid Cerebrovascular Events through Systematic Electronic Tracking and Tailoring of an Eminent Risk-factor (PACESETTER)

baseline characteristics between the IG and CG. These adjustments will help describe likely pathways by which the treatment influenced outcome. Additional analyses will assess patients' adherence to intervention and any secondary outcomes. We will adjust self reported measures for potential measurement error using standard techniques.¹⁴⁴

E.5.7.2. Management

Data will be captured via REDCap (a free, secure, web-based application) and overseen by a data management and analysis team comprising statisticians at MUSC. Data will be collected and sent electronically in password-encrypted files from the various sites to the team at MUSC. Secondary measures and demographics will be de-identified and sent to MUSC for double entry and comparison. Data will be reviewed on a bimonthly basis and issues will be communicated to the project coordinators. In particular outlying and inconsistent data values, as well as missing data, will be the targets of the data quality review.

E.6. Data Safety Monitoring Board (DSMB):

Given the minimal risk associated with the intervention, we will utilize an internal Data Safety Monitoring Board (DSMB) with the addition of one external member. The member extraneous to the project will be an experienced academic stroke attending neurologist based at an institution outside of South Carolina. The DSMB will meet twice per year to review study progress, e.g., recruitment, retention, drop out as well as possible adverse events.

E.7. PACESETTER (Specific Aim 4)

- Aim 4: To qualitatively explore provider effects of implementing the PACESETTER intervention vs. usual care, on the provider practice setting using focused ethnography.^{145,146}

E.7.1. Procedures

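### Adjusting for baseline characteristics cannot describe pathways of the treatment effect, and no planned model links the post-randomisation measures to the SBP effect

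*Combined protocol and SAP*

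**What the plan says.** The rule is in the combined protocol and SAP, section E.5.7.1 (Analysis), in a sentence that runs over a page break.

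- **Trigger:** "If statistically significant differences are found between IG and CG arms".
- **Action:** the plan will then run "regression analyses further adjusted by variables selected based on a combination of clinical judgment and descriptive statistical findings comparing" what the next page gives as "baseline characteristics between the IG and CG".
- **Stated purpose:** "These adjustments will help describe likely pathways by which the treatment influenced outcome".

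Section E.5.6.1 says patients are "randomly assigned to PACESETTER intervention vs. usual care in a 1:1 allocation ratio, stratified by race (Black and White) & study site".

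Section E.5.5 says "Potential mediator/moderators of risk factor control will also be collected" and does not separate the two roles. In Table 3 the Mediators block opens with age, education, income and depression, marked at baseline and not applicable at 4, 8 and 12 months. The next row of the block has hypertension/stroke knowledge, health literacy, disability and study site at every visit. Medication adherence and self-management are secondary outcomes at baseline and at 4, 8 and 12 months. Section E.5.5.2 adds a medication possession ratio (MPR) for all subjects.

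**The concern.** How a treatment works is a question about what happens after assignment: treatment changes an intermediate variable, and that variable changes the outcome. The planned step adjusts for variables picked from a comparison made before treatment starts. The first link is then missing by design, so the regression does not address the purpose given for it.

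The risk lies in interpretation. In any one trial the treatment coefficient will move somewhat when a prognostic baseline variable is added, because the arms are never perfectly balanced. Choosing variables partly by how much the arms differ favours those with the largest chance imbalance. A reader told that the adjustment describes pathways could take that movement as evidence that, say, income or baseline depression explains part of the benefit.

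The variables that could lie on a pathway are measured after randomisation and compared between arms, but no planned model connects them to the SBP difference.

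**Working it through.** The plan gives no figure for this step, so there is none to reproduce. The check is a logical argument, an illustration of its size and a comparison of passages.

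**1. Logic.** Let A be arm, X a baseline variable, M a post-randomisation variable and Y the 12-month SBP. The effect of A carried by a variable needs a link from A to that variable. X is fixed before A is assigned, so the A-to-X link is zero. For M it can be non-zero.

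**2. Simulation.**
- From E.5.6.2: 80 per arm and a total effect of -8.8 mm Hg.
- Assumed, because the documents give no values: X and the noise in M are standard normal; M = 1.0A + 0.5X + noise; X acts directly on Y at -4 mm Hg per SD; residual SD is 10 mm Hg; there is no unmeasured mediator-outcome confounding.
- With s the mediated share: Y = -8.8(1 - s)A - 8.8sM - 4X + error. There were 5,000 trials per row.

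| True mediated share | Unadjusted | Adjusted for X | Adjusted for X and M |
|---|---|---|---|
| 0% | -8.83 | -8.82 | -8.80 |
| 50% | -8.85 | -8.81 | -4.40 |
| 100% | -8.79 | -8.79 | 0.00 |

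The third column is the planned kind of adjustment. It gives the same answer whether none or all of the effect is mediated. The last column separates the three cases, but only because the model assumes no mediator-outcome confounding.

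**3. Chance movement in one trial.** Adding X moves the coefficient by about (total slope of Y on X) × (difference in mean X between arms). The SD of that mean difference is √(2/80) = 0.158 in SD units of X. The total slope is -4 - 8.8 × s × 0.5.

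- 0%: 4.0 × 0.158 = 0.63 (simulated 0.65)
- 50%: 6.2 × 0.158 = 0.98 (simulated 1.00)
- 100%: 8.4 × 0.158 = 1.33 (simulated 1.34)

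Among the roughly 5% of trials in which X was imbalanced at about p<0.05, the SD of the movement rose to 1.5, 2.3 and 3.1 mm Hg.

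**4. The same formula with the plan's own inputs.** Take X to be baseline SBP, with the stated correlation of 0.8 and equal SDs at baseline and 12 months (an assumption). The movement then has SD 0.8 × SD × 0.158.

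- With the SD implied by the effect size, 8.8/0.5 = 17.6 mm Hg: 0.8 × 17.6 × 0.158 = 2.2 mm Hg.
- With the quoted registry SD of 10.3 mm Hg: 0.8 × 10.3 × 0.158 = 1.3 mm Hg.

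This applies if baseline SBP is not already in the model. None of the movement is a pathway.

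**5. Passages side by side.** Earlier in E.5.7.1 the plan already adjusts all outcomes for baseline factors found imbalanced after randomisation, and compares that with an unadjusted analysis. There the purpose is correctly given as handling residual baseline differences. The later step makes much the same kind of adjustment but is said to describe pathways.

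**The case against.** The strongest defence is that the selection rule also includes clinical judgment, which could admit post-randomisation variables. That is possible. But the plan names none, and the only data source it states is the baseline comparison. The rule is under-specified, and its plain reading is baseline-only.

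It can also be said that the sentence is exploratory and promises only to help describe likely pathways, that no stated aim is a mediation aim, and that the Table 3 heading is a loose label for a mixed list. All of this is fair. It limits the weight of the point without making the sentence correct.

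The simulation coefficients are assumed and there is no confounding in it, which flatters the mediation model. That also stands. The conclusion rests on randomisation, and no mediated share can be quoted for this trial.

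Three stronger readings are tempting, and the documents do not support them.

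- **Conflict with B.8.** A reader might infer that the significance trigger contradicts the statement in B.8 that "even if PACESETTER has no effect, pre-planned analyses will allow us to discriminate aspects of the intervention". B.8 does not tie that promise to this regression. The subgroup analyses, the mixed models, the adherence analyses, the process evaluation in Table 4 and the Aim 4 ethnography carry no such trigger.
- **Measures not used.** A reader might infer that adherence, self-management and knowledge are collected and then ignored. Table 3 gives all three a target of group differences, and E.5.7.1 models all outcomes and analyses adherence. Only a model linking them to the SBP effect is absent.
- **Theory untested.** For the same reason, the links from treatment to adherence and to self-management are examined. The missing part is the link onward to SBP.

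**Conclusion.** The point holds in a limited form. As written, the step cannot support its stated purpose: the expected share of a randomised effect carried by a baseline variable is zero, whatever coefficients are assumed. Under the assumptions shown, chance movement has an SD of about 0.6 to 1.3 mm Hg for a generic prognostic covariate. It is 1.3 to 2.2 mm Hg for baseline SBP on the plan's own inputs, against a target difference of 8.8 mm Hg. The baseline-only rows of Table 3 should not be called mediators.

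The primary SBP comparison, its sample size and its p value are unaffected. The defect is in the analysis text, since candidate mediators are already scheduled for collection.

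**What to change.** **Minimum.** In E.5.7.1, restate the purpose of this regression as covariate adjustment for precision or chance imbalance, and delete the pathway sentence. In Table 3, relabel age, education, income and depression as moderators or covariates. Study site belongs with them, as it is a stratification factor. This costs only an edit.

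**If pathways are to be described.** Replace the step with a prespecified exploratory mediation analysis of 12-month SBP that:

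- uses mediators measured in both arms after randomisation and before month 12, namely MPR, self-management and hypertension/stroke knowledge at months 4 and 8;
- uses MPR for adherence, because the electronic-tray score that is the intervention arm's primary adherence measure is not described for controls;
- adjusts for baseline SBP and the baseline value of each mediator. The plan should confirm that a baseline MPR will exist, since E.5.3.1 speaks of follow-up evaluations while Table 3 marks adherence at baseline;
- states the direct and indirect effects to be estimated, and how month-4 variables that may confound month-8 mediators are handled;
- runs whatever the primary p value;
- includes a sensitivity analysis for mediator-outcome confounding.

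The cost is modest extra analysis on data already planned. The results would rest on an untestable no-confounding assumption. These mediators would also not cover the provider route (reduced therapeutic inertia), and Table 3 has no separate measure of self-efficacy or autonomous regulation. The write-up should state both limits.
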